5.1. Inclusion Criteria

- 5.1.1 Diagnosis of O-AML that is refractory to or intolerant to standard therapy and is no longer likely to respond to such therapy (at least one line of therapy); or
Diagnosis of MDS/CMML that is refractory to or intolerant to standard therapy and is no longer likely to respond to such therapy (at least one line of therapy)
- 5.1.2 Confirmed histologic diagnosis on bone marrow biopsy and aspirate within 28 days of trial entry prior to starting cycle 1.
- 5.1.3 Platelets $> 10 \times 10^9/L$
- 5.1.4 Age ≥ 18 years
- 5.1.5 ECOG performance status of 0, 1 or 2 (appendix III).
- 5.1.6 Prior systemic chemotherapy, immunotherapy, or biological therapy, radiation therapy and/or surgery are allowed; prior use of systemic methotrexate > 1 month prior to study entry is allowed. Intrathecal methotrexate is allowed prior to and during treatment per investigator discretion.

Time since prior therapy and the first dose of study drug:

- 5.1.7 At least 2 weeks since prior radiation, non cytotoxic small molecule drugs, prior major surgery (defined as a surgery involving a risk to the life of the patient; specifically: an operation upon an organ within the cranium, chest, abdomen, or pelvic cavity), prior systemic FDA-approved therapy
- 5.1.7 Patient must have recovered from the acute toxic effects (\leq grade 1 CTCAE v.4.0) of previous anti-cancer treatment prior to study enrollment; the only exception is that grade 2 neuropathy is permitted

- 5.1.8 Adequate organ function within 14 days of study registration defined as:

System	Laboratory Values
Hematologic	
Platelets	$> 10 \times 10^9/L$
Hepatic	
Bilirubin total	$\leq 1.5 \times ULN$
Alkaline Phosphatase, AST and ALT	$\leq 3 \times ULN$ ($< 5 \times ULN$ is acceptable if liver has tumor involvement)
Renal	
Serum Creatinine, or Creatinine Clearance, or GFR, or 24 hour urine creatinine clearance	$\leq 1.5 \times ULN$ $\geq 60 \text{ mL/min}$ $\geq 60 \text{ mL/min}$ $> 50 \text{ mL/min}$

- 5.1.9 Negative serum pregnancy test in females. Male and female patients with reproductive potential must use an approved contraceptive method if appropriate (for example, abstinence, oral contraceptives, implantable hormonal contraceptives, or double barrier methods) during, and for 3 months after the last dose of 765IGF-MTX.
- 5.1.10 Voluntary written informed consent before performance of any study-related procedure not part of normal medical care, with the understanding that consent may be withdrawn by the patient at any time without prejudice to future medical care.

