8.1. Standard of Care Procedures

	Baseline, within 28 days of enrollment	Each treatment cycle ^a			Every 8 weeks (± 1 week)	30 days (± 1 week) after final dose of 765IGF-MTX ¹
		Day 1 ² (±1 day)	Day 8 (±1 day)	Day 15 (±1 day)		
Signed consent (Registration/ Enrollment must occur within 30 days.)	X					
Medical history	X	X				X
Review of prior therapy	X					
Bone marrow biopsy and aspirate confirming disease and blast count ³	X				X ³	
Physical exam	X	X				X
Vital signs	X	X	X	X		X
Height, weight	X	X				X
Concomitant meds review	X	X	X	X		X
Performance status	X	X				X
Symptom and toxicity	X	X	X	X		X ³
CBC w/ diff	X	X	X	X		X
CMP (with: calcium, glucose, sodium, potassium, CO ₂ , chloride, BUN, creatinine, albumin, ALT, AST, bilirubin, alkaline phosphatase, total protein)	X	X	X	X		X
Uric acid (cycle 1 only)	X	X		X		
LDH	X	X				
HbA1C for diabetic patients	X					X
Serum pregnancy test for females of child- bearing potential	X					
ECG ⁴	X	X				X
765IGF-MTX administration			X	X		

^a Subsequent cycles beyond cycle 1 must meet the criteria found in section 7.3 and may begin 1 day earlier or up to 2 days later to accommodate scheduling issues.

¹ For patients who leave treatment with a response, repeat appropriate disease assessment every 6-12 weeks until progression or start of a new treatment.

² For cycle 1 only, tests and procedures do not need to be repeated if done within 3 days of day 1.

³ Bone marrow biopsy should be at end of end of cycle 2, and every 2 cycles thereafter to cycle 6. Patients who achieve response (CR) could have repeat bone marrow biopsies per MD discretion.

⁴ ECG performed at screening, at cycle 1 and at the end of study visit 30 days after the final dose.

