Appendix I – Response Criteria for Acute Leukemia

Acute Myeloid Leukemia⁴⁵

Table 5. Response criteria in AML

Category	Definition
Complete remission (CR)*	Bone marrow blasts < 5%; absence of blasts with Auer rods; absence of extramedullary disease; absolute neutrophil count $> 1.0 \times 10^9/L$ (1000/ μ L); platelet count $> 100 \times 10^9/L$ (100 000/ μ L); independence of red cell transfusions
CR with incomplete recovery (CRI)†	All CR criteria except for residual neutropenia ($< 1.0 \times 10^9/L$ [1000/ μ L]) or thrombocytopenia ($< 100 \times 10^9/L$ [100 000/ μ L])
Morphologic leukemia-free state‡	Bone marrow blasts < 5%; absence of blasts with Auer rods; absence of extramedullary disease; no hematologic recovery required
Partial remission (PR)	Relevant in the setting of phase 1 and 2 clinical trials only; all hematologic criteria of CR; decrease of bone marrow blast percentage to 5% to 25%; and decrease of pretreatment bone marrow blast percentage by at least 50%
Cytogenetic CR (CRC)§	Reversion to a normal karyotype at the time of morphologic CR (or CRI) in cases with an abnormal karyotype at the time of diagnosis; based on the evaluation of 20 metaphase cells from bone marrow
Molecular CR (CRM)¶	No standard definition; depends on molecular target
Treatment failure	
Resistant disease (RD)	Failure to achieve CR or CRI (general practice; phase 2/3 trials), or failure to achieve CR, CRI, or PR (phase 1 trials); only includes patients surviving ≥ 7 days following completion of initial treatment, with evidence of persistent leukemia by blood and/or bone marrow examination
Death in aplasia	Deaths occurring ≥ 7 days following completion of initial treatment while cytopenic; with an aplastic or hypoplastic bone marrow obtained within 7 days of death, without evidence of persistent leukemia
Death from indeterminate cause	Deaths occurring before completion of therapy, or < 7 days following its completion; or deaths occurring ≥ 7 days following completion of initial therapy with no blasts in the blood, but no bone marrow examination available
Relapse	Bone marrow blasts $\geq 5\%$; or reappearance of blasts in the blood; or development of extramedullary disease

Table 6. Outcome measures in AML

Category	Definition
Overall survival	Defined for all patients of a trial; measured from the date of entry into a study to the date of death from any cause; patients not known to have died at last follow-up are censored on the date they were last known to be alive

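### The baseline marrow may predate the last prior therapy, so a blast fall caused by that therapy can, though probably seldom, count as a 765IGF-MTX response

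*Combined protocol and SAP*

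**What the plan says.** **Marrow timing.** Section 5.1.2 requires "Confirmed histologic diagnosis on bone marrow biopsy and aspirate within 28 days of trial entry prior to starting cycle 1". In the 8.1 schedule, the row "Bone marrow biopsy and aspirate confirming disease and blast count" falls under the column "Baseline, within 28 days of enrollment". The research table in 8.2 also allows 28 days but counts back from cycle 1 day 1 (C1D1).

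**Prior therapy.** The intervals come under the line "Time since prior therapy and the first dose of study drug". The first of the two items numbered 5.1.7 reads "At least 2 weeks since prior radiation, non cytotoxic small molecule drugs, prior major surgery", and its list ends with "prior systemic FDA-approved therapy". One drug has a longer interval, in 5.1.6: "prior use of systemic methotrexate > 1 month prior to study entry is allowed".

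**Use of the baseline.** Appendix I (Table 5) requires, for AML PR, a "decrease of pretreatment bone marrow blast percentage by at least 50" percent. Appendix II uses the same relative fall for MDS PR and marrow CR. Section 3.2.2 treats marrow CR as equivalent to CRi, and 13.2.1 counts best responses of CR, CRi or PR as overall remissions. Section 13.2 takes as baseline the last value measured before the first dose.

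**What is absent.** No section places the baseline marrow after the last prior dose, or provides for the case where therapy is given after it. The bar on other anti-cancer therapy in 7.6 applies during study treatment, not during screening. The 14-day rule in 6.3 applies only to patients who are rescreened.

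**The concern.** The marrow window and the prior-therapy interval run from different anchors and have different lengths. A patient can have the screening marrow, receive more prior therapy, stop 2 weeks before dosing and still be eligible. If no later marrow is taken, the older blast count is the comparator for every response defined by a relative fall. Any drop that the intervening therapy produced is then scored together with the drop on 765IGF-MTX.

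Clinical benefit is the study's secondary objective, and there is no control arm that would reveal carry-over. Section 13.4.2 reports responses by dose and disease, and some dose levels may hold a single patient. One misattributed response could be the whole result for such a cell.

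**Working it through.** The plan gives no figure for this point, so there is none to reproduce. The check is on the windows, the criteria and the weight of one case.

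**1. Overlap of the windows.** Inputs: marrow up to 28 days before entry or enrollment (5.1.2, 8.1); listed therapy up to 14 days before the first dose (5.1.7). Let g be the number of days from entry to C1D1. The documents set no maximum g for first-time enrollees, so the values above 0 are assumptions.

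Overlap = (28 + g) − 14

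| g (days) | Marrow age at first dose | Prior therapy possible after the marrow |
|---|---|---|
| 0 | 28 | 14 |
| 3 | 31 | 17 |
| 7 | 35 | 21 |
| 14 | 42 | 28 |

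If the anchor in 8.2 governs, the overlap is 14 days whatever g is. For systemic methotrexate there is no overlap, because its interval exceeds one month before entry and the marrow falls within 28 days of entry.

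**2. Which responses depend on the baseline count.**

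| Response | Needs a ≥50% fall from pretreatment? | Also needs blood-count criteria? |
|---|---|---|
| AML CR | No (absolute threshold) | Yes |
| AML CRi | No (absolute threshold) | Incomplete count recovery accepted |
| AML PR | Yes | Yes |
| MDS CR | No (absolute threshold) | Yes |
| MDS PR | Yes | Yes, where abnormal before treatment |
| MDS marrow CR | Yes, with blasts ≤5% | No |

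MDS marrow CR is the main exposure, because there a blast fall is sufficient without blood-count recovery.

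**3. Illustration with assumed blast counts.** Take an MDS patient with 8% at day −28, 4.5% just before dosing after further prior therapy, and 4% at the end of cycle 2.

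- Against the day −28 marrow: (8 − 4)/8 = 50%. Marrow CR is met if the response lasts 4 weeks.
- Against a pre-dose marrow: (4.5 − 4)/4.5 = 11%. Marrow CR is not met.

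**4. Time for a carried-over fall to persist.** The first response marrow is at 8 weeks ± 7 days (7.2.1), so 49 to 63 days after the first dose. Prior therapy ending on day −14 puts it 14 + 49 = 63 to 14 + 63 = 77 days after the last prior dose.

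**5. Weight of one case.** Section 4 plans 9 patients at the MTD. One response is 1/9 = 11.1% (exact 95% CI 0.3% to 48.2%). Without it the rate is 0/9 = 0% (0% to 33.6%).

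**6. Frequency.** The documents give no rate. Let f be the share of patients treated after their marrow and r the chance that such a patient is falsely scored a responder. The chance of at least one case among 9 is 1 − (1 − f·r)^9:

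- f = 10%, r = 5%: 4%
- f = 25%, r = 10%: 20%
- f = 50%, r = 20%: 61%

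All f and r are assumed. The last pair is hard to square with patients selected as unlikely to respond.

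**The case against.** The strongest reply is that eligibility largely excludes the scenario. Under 5.1.1 patients must be refractory or intolerant and, in either case, judged unlikely to respond further to standard therapy. A patient whose blasts are halving on such therapy does not plainly qualify. A carried-over fall would also have to persist 63 to 77 days, and MDS responses must last at least 4 weeks (Appendix II). PR needs blood-count criteria as well, and the CR categories rest on absolute thresholds. All of this stands, and it is why the error should be uncommon. None of it changes the comparator when the error does occur: unlikely to respond is a judgement, not a marrow rule.

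It is also fair that 1/9 is the weight of any single misclassification at n = 9, and that 14 of 28 days is calendar arithmetic. A reader might infer that half of patients are exposed, or that carry-over is in fact being counted as response. The documents support neither; they show only that it can happen.

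Finally, requiring a post-therapy marrow from everyone would not cure the problem. A marrow on day −13 after therapy ending on day −14 would comply, yet a later effect of that therapy would still be credited to 765IGF-MTX. It could also force a second biopsy on patients already sampled. That objection stands and limits the fix.

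**Conclusion.** The gap is real and its reach is limited. With entry on C1D1, up to 14 days of listed prior therapy can fall between the baseline marrow and dosing, and more if entry precedes C1D1. AML PR, MDS PR and mainly MDS marrow CR can then be scored against a blast count that predates that therapy. This is probably seldom, but one case moves the observed ORR at the MTD by 11 percentage points and could decide a dose-by-disease cell.

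A reader might extend this to dose selection. That does not follow: the MTD rests on cycle 1 DLTs and does not use response, which is secondary and descriptive. The conclusion assumes that some patients have only one pre-dose marrow and receive listed therapy after it. The plan permits this but gives no frequency.

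**What to change.** **In 13.2.1 (and the full SAP still to be finalized):**
- Record the baseline marrow date against the date of the last prior anti-cancer dose.
- Flag patients whose marrow came first, and report ORR with and without baseline-dependent responses (AML PR, MDS PR, MDS marrow CR) in those patients.
- Where more than one pre-dose marrow exists, use the one taken after the last prior therapy. The last-value rule in 13.2 already points this way; state it explicitly for response scoring.

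**In 5.1.2 and 8.1:** state that a screening marrow not yet done is scheduled after the last prior anti-cancer dose, without requiring a repeat biopsy where one has been done. Reconcile the 28-day anchors in 5.1.2 (entry), 8.1 (enrollment) and 8.2 (C1D1).

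**In 5.1.7:** the list does not clearly cover agents that are not FDA-approved and fall outside its other classes. The sponsor should clarify which therapies the interval covers. No interval is proposed here.

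**Cost.** A little more analysis work and, for a few patients, a screening marrow some days later. The inputs are largely collected already through the prior-therapy review in 8.1 and the medication history in 7.5. The change reduces carry-over bias but does not eliminate it.

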5.2. Exclusion Criteria

- 5.2.1. ECOG PS >2.
- 5.2.2. Patients with active extramedullary disease.
- 5.2.3. Active CNS involvement.
- 5.2.4. Pleural effusions or ascites.
- 5.2.5. \geq Grade 3 peripheral neuropathy within 14 days before enrollment.
- 5.2.6. Active uncontrolled infection or severe systemic infection (enrollment is possible after control of infection).
- 5.2.7. Myocardial infarction within ONE months prior to enrollment or has New York Heart Association (NYHA – appendix IV) Class III or IV heart failure, uncontrolled angina, severe uncontrolled ventricular arrhythmias, or electrocardiographic evidence of acute ischemia or active conduction system abnormalities. Prior to study entry, any ECG abnormality at screening has to be documented by the investigator as not medically relevant.
- 5.2.8. Pregnant or breastfeeding – methotrexate is Pregnancy Category X - has been reported to cause fetal death and/or congenital abnormalities. Confirmation that the subject is not pregnant must be established by a negative serum β -human chorionic gonadotropin (β -hCG) pregnancy test result obtained during screening. Pregnancy testing is not required for post-menopausal or surgically sterilized women.
- 5.2.9. Uncontrolled diabetes mellitus defined as a Hemoglobin A₁C $\geq 10\%$ in patients with a prior history of diabetes, prior to study enrollment.

- 5.2.10. Serious concomitant systemic disorders (e.g., active uncontrolled infection or uncontrolled diabetes) or psychiatric disorders that, in the opinion of the investigator, would compromise the safety of the patient or compromise the patient's ability to complete the study.
- 5.2.11. Other severe acute or chronic medical or psychiatric conditions, or laboratory abnormality that may increase the risk associated with study participation or investigational product administration or may interfere with the interpretation of study results and, in the judgment of the investigator, would make the patient inappropriate for enrollment in this study.
- 5.2.12. Any history of epilepsy or a seizure disorder or any known prior seizures.
- 5.2.13. Abnormalities on 12-lead electrocardiogram (ECG) considered by the investigator to be clinically significant.
- 5.2.14. Known immediate or delayed hypersensitivity reaction or idiosyncrasy to drugs chemically related to IGF or methotrexate.

6. Registration/Enrollment

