7.5. Concomitant Medications and Non-Drug Therapies

All patients will be asked to provide a complete list of prescription and over-the-counter medications that have been taken within the 4 weeks prior to screening. The investigator must be informed as soon as possible about any new medication(s) taken from the time of screening until the completion of the post-treatment follow-up visit.

7.6. Prohibited Concomitant Medications and Concomitant Medications to be used with caution.

The only prohibited concomitant medications are mercaptopurine, and concomitant other anti-cancer therapy (cytotoxic, biologic, or radiation).

Concomitant use of salicylates, sulfonamides, BACTRIM (trimethoprim/sulfamethoxazole) and phenylbutazone is not prohibited, but should be used with caution because of their interactions with high dose methotrexate (doses greater than or equal to 500mg/m² of methotrexate are considered high), although the methotrexate doses used in this study are not high (the highest dose of 765IGF-MTX used in this study of 2.5 microEq/kg is about equal to 45 mg of methotrexate per meter²).

Patients should not receive other anti-cancer therapy (cytotoxic, biologic, or radiation) while on treatment in this study.

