9.1.2. Pharmacokinetic Sample Processing

Blood samples (6 mL) will be collected in 6-mL EDTA (purple top) tubes. The tube should be gently inverted a few times for complete mixing with the anticoagulant. The exact time of sample collection should be recorded on the tube label and Pharmacokinetics Data Form provided. The tube should be kept on wet ice until centrifugation. Within 120 minutes of blood collection, centrifuge each blood sample at approximately 3,000 X g for 5-10 minutes at 4°C. Aliquots, approximately 0.5 mL each, will be pipetted into 4 separate plastic centrifuge tubes and frozen at -80°C until analysis. Please see the laboratory manual for PK sample collection procedures.

765IGF-MTX, 765IGF, methotrexate and 7-OH-methotrexate plasma concentrations will be determined using validated assays under GLP conditions at the Toxicology Research Laboratory, University of Illinois at Chicago.

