Appendix V – Prohibited Concomitant Medications

Mercaptopurine
Concomitant other anti-cancer therapy (cytotoxic, biologic, or radiation)

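### Section 5.1.6 allows intrathecal methotrexate during treatment while Section 7.6 and Appendix V bar concomitant cytotoxics; any such use could confound free-drug PK and cycle 1 DLT counts

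*Combined protocol and SAP*

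**What the plan says.** All references are to the combined protocol and SAP.

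- **Permission.** Section 5.1.6 says "Intrathecal methotrexate is allowed prior to and during treatment per investigator discretion". It sets no limit on dose, cycle or distance from a sampling day. The same criterion sets a gap for the systemic route ("prior use of systemic methotrexate > 1 month prior to study entry is allowed") but none for the intrathecal route.
- **Prohibition.** Section 7.6 says "Patients should not receive other anti-cancer therapy (cytotoxic, biologic, or radiation) while on treatment in this study". It also names other anti-cancer therapy as one of only two prohibited concomitant categories, the other being mercaptopurine. Appendix V repeats both. Neither place exempts the intrathecal route.
- **PK.** Section 9.1.2 says "765IGF-MTX, 765IGF, methotrexate and 7-OH-methotrexate plasma concentrations will be determined using validated assays". Sections 3.3.1 and 9.1.4 treat each of the four as an analyte in its own right. Sampling is on cycle 1 days 1 and 15, at the MTD only, in at least 3 patients (Section 4; Section 8.2, footnote 1).
- **DLTs.** Section 4 lists four criteria for cycle 1. Two require the event to be related to treatment: prolonged grade 4 hematologic toxicity, and grade 3 or greater non-hematologic toxicity. Febrile neutropenia, and platelets below 10 × 10⁹/L with clinically significant bleeding, carry no such qualifier.
- **Exclusion.** Section 5.2.3 excludes "Active CNS involvement".

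**The concern.** A site cannot satisfy both rules. An investigator who acts on 5.1.6 can be recorded as deviating from 7.6, and one who acts on 7.6 is withholding something that 5.1.6 leaves to the investigator's judgement.

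The conflict reaches the analysis because the permitted drug is the one the conjugate carries. Methotrexate from a second source is the same molecule as methotrexate released from the conjugate, and the plasma assay cannot tell them apart. Section 9.1.3 plans models that link parent and metabolite, and a comparison of the first dose with later doses to look for antibody effects. For the free-drug analytes, an unrecorded second source would disturb both.

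In dose finding, a methotrexate-type toxicity in cycle 1 would have two candidate causes. Section 10.1.9 itself names the intrathecal route among those after which skin reactions have occurred. No section says how such a patient's PK profile or DLT evaluation is to be handled.

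**Working it through.** **1. Is there an exception that resolves the conflict?** Section 5.1.6 permits use during treatment. Section 7.6 prohibits cytotoxic therapy for the whole time on treatment, and Appendix V does so again. None of the three refers to another or states which takes precedence. The conflict stands.

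**2. How much of the PK could one patient affect?** Inputs: 3 patients (the minimum), 2 sampling days and 4 analytes, of which 2 are free drug.

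- All profiles: 3 × 2 × 4 = 24. Free-drug profiles: 3 × 2 × 2 = 12.
- One patient affected on both days: 1 × 2 × 2 = 4 profiles, which is 4/12 = 33% of the free-drug profiles and 4/24 = 17% of all profiles.
- One patient affected on one day: 2 profiles, which is 2/12 = 17% and 2/24 = 8%.

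If more than 3 patients are sampled, these shares fall.

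**3. What can one extra DLT do?** Section 4 opens further cohorts after 3 of 3, 5 of 6 or 7 of 9 patients complete cycle 1 without DLT, so at most 0, 1 or 2 DLTs are allowed. It defines the MTD by a DLT rate below 33%.

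| Without the event | With it | Consequence |
|---|---|---|
| 0/3 | 1/3 | 3 of 3 not met |
| 1/6 | 2/6 | 5 of 6 not met |
| 2/9 = 22.2% | 3/9 = 33.3% | 7 of 9 not met, and the rate is not below 33% |

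Before that stage, one drug-related toxicity of grade 2 or higher (alopecia, nausea and diarrhea excepted) ends single-patient cohorts.

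**4. Scale, by administered dose only.** Section 10.1.5 equates 1 µeq with 1 µmol of methotrexate groups. The molar mass is assumed to be 454.44 g/mol.

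Check against the plan's own figure in Section 7.6 (2.5 µEq/kg is about 45 mg/m²): 2.5 × 0.45444 = 1.136 mg/kg. Multiplied by an assumed 37 to 40.5 kg/m², this gives 42.0 to 46.0 mg/m². The stated figure reproduces.

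Content per infusion in mg = dose × weight × 0.45444, with an assumed weight of 70 kg. The documents give no intrathecal dose; 6 to 15 mg is assumed.

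| Level | µEq/kg | mg per infusion | 6–15 mg as % of content |
|---|---|---|---|
| 1 | 0.20 | 6.4 | 94–236% |
| 2 | 0.40 | 12.7 | 47–118% |
| 3 | 0.80 | 25.4 | 24–59% |
| 4 | 1.6 | 50.9 | 12–29% |
| 5 | 2.5 | 79.5 | 8–19% |

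Weight moves these figures. At level 1 the range is 132–330% for 50 kg and 73–183% for 90 kg; at level 5 it is 11–26% and 6–15%. For PK, only the row that turns out to be the MTD is relevant.

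**The case against.** The best reply is that 5.1.6 is a specific and deliberate permission and 7.6 a general rule, so the natural reading is an exception that was never carried across. That is plausible and would make this an error of cross-reference. But the text does not say so, and sites should not have to infer it.

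The second reply is that the consequences are conditional, and this stands. Use is discretionary, and excluding active CNS involvement should make it uncommon. Harm to PK needs a dose close to day 1 or day 15 in one of the sampled patients. A reader might infer that the free-drug PK will be contaminated, or that one patient spoils a third of the PK data. The documents support neither: 765IGF-MTX and 765IGF are not directly affected, and one third is the ceiling for two analytes at the minimum sample.

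A reader might also take the percentages above as relative exposure. They compare an injected dose with methotrexate bound in the conjugate. Plasma free methotrexate from either source is not in the documents, so the ratio could mislead in either direction.

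Finally, some safeguards exist. Concomitant medications are reviewed at baseline, on days 1, 8 and 15, and at the final visit (Section 8.1). Attribution is recorded for every toxicity (Section 11.2), so saying that toxicity cannot be attributed would go too far. The pre-infusion PK sample would show methotrexate left from an earlier dose, though not a dose given within the sampling window. Section 13 defers complete analysis details to a full SAP, so a handling rule may yet be written. None of this supplies one now, and attribution grading does not help with the two DLT criteria that ignore cause.

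**Conclusion.** The contradiction between 5.1.6 and both 7.6 and Appendix V is certain and needs only the text to establish. Its effect on the results is possible rather than expected. In a patient given intrathecal methotrexate near PK sampling or during cycle 1, plasma methotrexate and 7-OH methotrexate could be confounded, and toxicity would be harder to attribute. The size is at most one third of the profiles for those two analytes per affected patient when 3 are sampled, and one DLT in cohorts where a single event can decide the gate. That any confounder could do the same in cohorts this small is true, but here the protocol itself admits the confounder.

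The milligram comparison rests on assumed weight, molar mass and intrathecal dose. It shows only that the outside dose need not be trivial beside the conjugate's content at low levels. Frequency of use and systemic exposure remain unknown. The point is worth correcting because the correction is cheap, not because large damage is likely.

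**What to change.** 1. Reconcile Section 5.1.6 with Section 7.6 and Appendix V, so that all three state the same rule. The choice of rule is a clinical matter for the sponsor and investigators.
2. Whatever the rule, capture the date and dose of any intrathecal methotrexate that is given, through the existing concomitant medication review.
3. In the full SAP, define before database lock what makes a methotrexate or 7-OH methotrexate profile affected, using the recorded date and dose and the pre-infusion concentration. Exclude affected profiles from the main PK summaries and list them separately. Keep the 765IGF-MTX and 765IGF profiles of the same patients.
4. Flag affected patients in the cycle 1 DLT table, so that a reader can see whether a cohort decision turned on one of them.

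The cost is a wording amendment, explicit date and dose entries, and a short SAP paragraph. The downside is that a few free-drug profiles may be lost from an already small PK set; listing them separately keeps them visible.

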3.3.4 Plasma 765IGF Level and 765IGF-MTX toxicity/response

3.3.5 Plasma and whole blood IGF-1R level and 765IGF-MTX Toxicity/Response

3.3.6 Assess formation of antibodies against 765IGF-MTX

3.3.7 Assess formation of neutralizing antibodies

3.3.8 IGF-1R expression level in diseased tissue in bone marrow, as measured by IHC, and flow cytometry, and in blood cells as measured by flow cytometry.

4. Overall Design and Study Plan

This pilot study will evaluate the safety and clinical benefit of 765IGF-MTX in patients with advanced, previously treated MDS, CMML or O-AML. 765IGF-MTX is administered as an IV infusion over 1.5 hours on days 1, 8 and 15 of a 28 day cycle. Treatment continues until disease progression, unacceptable toxicity, or patient refusal. Assessment of response will be confirmed with bone marrow studies performed at the end of cycle 2, and every 8 weeks +/- 7 days (2 cycles) thereafter up to the end of cycle 6, and at physician's discretion thereafter.

- Dose Finding Component: Up to 5 dose levels will be tested (refer to schema on page 6). The maximum tolerated dose (MTD) will be determined using the modified toxicity probability interval design with dose limiting toxicity (DLT) estimated at 0.33.

Our modification involves using cohorts of size 1 for the initial doses, which allows rapid escalation through the initial dose levels, and expanding to cohorts of size 3 once any grade 2 or higher toxicity is observed that is considered related to study drug (with the exception of alopecia, nausea, or diarrhea). Additional patient cohorts will not be enrolled until 1 of 1 (with no grade 2 toxicity), 3 of 3, 5 of 6, or 7 of 9 patients at the current dose level complete all planned treatment for cycle 1 (defined as 3 doses of 765IGF-MTX without DLT and are able to start cycle 2 with no more than a 2 week delay. At the discretion of the principal investigator, intra-patient dose escalation between cycles is also allowed but only after 2 cycles at one dose level and confirmation of safety in at least 3 patients treated at the higher dose level.

If none of the dose levels are acceptable at study completion, an optimal dose level will not be identified and the drug does not warrant further investigation.

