6.1. Registration/Enrollment with the Clinical Trials Office

Upon obtaining informed consent, completion of the screening evaluation, and verifying eligibility, the site study coordinator or designee will enroll the patient into EDC Easy®, the CTO Clinical Trials Management System (CTMS). The eligibility checklist must be completed by the study coordinator and verified/confirmed by the Principal Investigator or her designee (i.e., a sub-Investigator).

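### The 2-week interval before the first dose omits unapproved cytotoxics and unapproved biologics, a narrow patient-safety gap of unknown frequency

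*Combined protocol and SAP*

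**What the plan says.** All the relevant eligibility text is in section 5.1.

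- **First 5.1.7.** At least 2 weeks must pass before the first dose after radiation, non-cytotoxic small molecule drugs, major surgery, and "prior systemic FDA-approved therapy".
- **5.1.6.** "Prior systemic chemotherapy, immunotherapy, or biological therapy, radiation therapy and/or surgery are allowed". This is not limited to approved agents. The one drug-specific interval is for methotrexate: "prior use of systemic methotrexate > 1 month prior to study entry is allowed".
- **Second 5.1.7.** "Patient must have recovered from the acute toxic effects" of earlier anti-cancer treatment, to grade 1 or less, before enrollment. Grade 2 neuropathy is the only exception.

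Elsewhere, 5.2.11 lets the investigator exclude a patient for a medical or psychiatric condition or a laboratory abnormality that "may interfere with the interpretation of study results" or raises risk. Section 6.1 has the eligibility checklist "verified/confirmed by the Principal Investigator or her designee". Section 7.5 asks for the medications taken in the 4 weeks before screening, and the section 8.1 calendar has a baseline row for review of prior therapy. Section 7.6 says "Patients should not receive other anti-cancer therapy (cytotoxic, biologic, or radiation) while on treatment in this study".

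**The concern.** The protocol treats 2 weeks as the least acceptable gap after an approved systemic agent. It gives no reason for asking less after an unapproved cytotoxic or biologic, whose delayed toxicity is likely to be less well described.

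The population makes the situation plausible. Criterion 5.1.1 enrolls patients whose disease is refractory to standard therapy, or who cannot tolerate it, and some of these may come from another trial. They may enter with platelets only just above 10 x 10^9/L, and 5.1.8 sets no neutrophil minimum. If the effects of two investigational agents overlap, such a patient has little marrow reserve. What is at stake is an avoidable hazard to an individual patient.

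**Working it through.** The protocol gives no figure to reproduce, and the point needs no sample size or error rate. The check is one of coverage: list each class of prior treatment and find the minimum interval that applies.

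| Prior treatment | Minimum interval | Source |
|---|---|---|
| Radiation | 2 weeks | first 5.1.7 |
| Major surgery | 2 weeks | first 5.1.7 |
| Non-cytotoxic small molecule, approved or not | 2 weeks | first 5.1.7 |
| FDA-approved systemic therapy, including approved cytotoxics and biologics | 2 weeks | first 5.1.7 |
| Systemic methotrexate | more than 1 month | 5.1.6 |
| Unapproved cytotoxic other than methotrexate | none stated | – |
| Unapproved biologic | none stated | – |

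The next step is to ask whether another provision supplies the missing interval.

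1. **Recovery rule (second 5.1.7).** It covers all earlier anti-cancer treatment, approved or not. It tests toxicity that is visible before enrollment. A cytotoxic given a few days before may not yet have produced its lowest counts, so a patient can satisfy the rule and worsen afterwards.
2. **Organ function (5.1.8).** It is measured within 14 days of registration and has the same limit: it records the state on the day of the test.
3. **Exclusions 5.2.1 to 5.2.14.** None names a prior investigational agent or a time. 5.2.11 is discretionary and is framed around conditions and laboratory findings, not recent treatment.
4. **Medication list (7.5).** It asks for prescription and over-the-counter drugs over 4 weeks. It should often bring recent exposure to light, but it does not name trial agents and attaches no waiting period to what is found.
5. **Baseline review of prior therapy (8.1).** The calendar gives a row label only, with no content and no rule.
6. **Checklist (6.1).** It verifies the criteria as written and cannot enforce an interval that is absent from them.
7. **Sections 6.2 and 6.3, 7.6 and Appendix V.** The enrollment and re-screening rules do not address prior agents. The ban on other anti-cancer therapy in 7.6 applies during study treatment, not before it.

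No provision fills the last two rows of the table. A patient treated with either class a few days earlier, and at grade 1 or less at enrollment, meets every stated criterion on timing.

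**The case against.** The strongest case on the other side is that the gap is small and already guarded. Four parts of that case deserve an answer.

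- **Narrowness.** Investigational non-cytotoxic small molecules are covered, as are all approved systemic agents. Nothing in the documents shows that any patient would come from a trial of an unapproved cytotoxic or biologic. This stands, and it limits the weight of the point.
- **Existing controls.** Recovery to grade 1 or less, the 4-week medication list and the baseline review make it unlikely that recent exposure passes unnoticed. This stands in part: noticing an exposure is not the same as having a rule about it.
- **The low-platelet scenario.** Severe thrombocytopenia caused by the recent agent would itself fail the recovery rule. Harm through this route requires the low count to be attributed to the disease and further toxicity to appear later. That is possible in MDS, but it is a chain of conditions.
- **Why 14 days?** Nothing shows that 2 weeks would capture delayed toxicity from an unknown agent. This stands. The proposal makes the protocol's own minimum apply consistently; it does not claim that this minimum is ideal.

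A reader might go further and infer that carry-over would distort the dose-limiting toxicity (DLT) count and so the MTD, which is "determined using the modified toxicity probability interval design with dose limiting toxicity (DLT) estimated at 0.33". There is some basis for the thought: in section 4, febrile neutropenia, and platelets below 10 x 10^9/L with bleeding, count as DLTs without a treatment-related qualifier. The documents do not support the inference as a material effect. They give no share of patients exposed and no rate of carried-over events, so any size would rest on invented inputs. The same two criteria can be met by the disease itself or by late effects of approved therapy. The missing attribution term is a separate matter that a washout change would not cure.

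**Conclusion.** The point holds as a narrow patient-safety gap. The first 5.1.7 sets no minimum interval after an unapproved cytotoxic other than systemic methotrexate, or after an unapproved biologic. The safeguards reduce the risk without setting a time and without reaching toxicity still to come.

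The contrast is 14 days for approved systemic therapy against no stated minimum for these two classes. How often it would matter is unknown, and no effect on the MTD is claimed. The conclusion rests on reading the FDA-approved qualifier literally, and on the absence of an interval in the eligibility, enrollment, concomitant-medication and calendar sections. It is worth correcting because the correction is cheap, not because harm has been shown to be likely.

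**What to change.** In the first 5.1.7, replace "prior systemic FDA-approved therapy" with: *any prior systemic FDA-approved therapy or investigational anti-cancer therapy (including cytotoxics and biologics)*. Keep the limit of more than 1 month for systemic methotrexate in 5.1.6, and carry the new wording into the eligibility checklist.

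The cost is one phrase in two places. A few patients arriving from another trial may wait up to 2 weeks for the first dose, which is a real consideration in advanced refractory disease. The change reduces carry-over but does not remove it, and no additional data collection or listing is needed.
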